## **Ethical considerations:**

- 1. An approval from the Research Ethics Committee of faculty of medicine will be obtained.
- 2. An informed written consent from all patients or first-degree relatives before participation will be obtained; it will include data about aim of the work, study design, site, time, subject and methods, confidentiality.
- 3. Official permission will be obtained from the Dean of Faculty of Medicine and the administrators of University Hospitals to conduct this study.

### **Results**

The results will be tabulated, correlated and statistically analyzed to fulfill the aim of the work.

#### Statistical analysis

We will use IBM's Statistical Package for the Social Sciences (2017, Released) to edit, code, and tabulate the data we gathered. IBM Corp., Armonk, New York, USA: IBM SPSS Statistics for Windows, Version 25.0. To ensure that the data was distributed normally, the Shapiro-Wilk test was employed. Each parameter's data type informed the presentation and analysis of the corresponding data. Nominal data were expressed as mean ± SD. For categorical data, percentages and frequencies were employed. The statistical significance of a difference between two study groups for parametric variables was assessed using an independent samples t-test, and for non-parametric variables, the Mann Whitney Test (U test) was employed. We looked examined the correlation between the two qualitative variables using the Chi-Square test. At a 95% confidence interval, a p-value is deemed significant if it is less than 0.05.

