## Aim of the Work

The aim of this study is to assess efficacy and tolerability of Silodosin 4mg vs Dapoxitine 60mg in treatment of primary premature ejaculation.

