#### **Inclusion Criteria:**

- Age > 18 years old.
- Patients with primary premature ejaculation (PPE) according to (IELT < 1 min)

- Sexually active.
- Heterosexual.
- The course of suffering from PE is  $\geq 6$  months.

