## Study design:

Patients who meet the previous criteria will be enrolled in the study.

We randomly assigned 80 outpatients with PPE to two groups , group A (sildosin 4mg) 40 patients and group B (dapoxatine 60mg) 40 patients .

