#### 2. Clinical Examination:

A thorough clinical examination of the patients will be conducted to evaluate their general health and assess any physical signs and symptoms related to premature ejaculation or other conditions.

Group A (sildosin 4 mg): intake 2h before intercourse (on demand) at least 6 times intercourse /month for 2 months.

Group B (dapoxatine 60mg): the same like sildosin.

**Follow up** patients will be evaluated by PEP (premature ejaculatory profile) & IELT. (intravaginal latency time) 2 months after start of treatment.

Intravaginal ejaculatory latency time (IELT): normal duration 2.5- 5 minutes. (Waldinger MD, et al .2005).

scores of the Premature Ejaculation Profile (PEP): to evaluate the reliability and validity of the Premature Ejaculation Profile (PEP), The

PEP contains four measures: perceived control over ejaculation, personal distress related to ejaculation, satisfaction with sexual intercourse, and interpersonal difficulty related to ejaculation, each assessed on five-point response scales. (Patrick DL, et al.,2009).

Any side effects of drugs will be recognized and recorded.

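### No primary efficacy outcome or multiplicity rule is named, so the result that decides efficacy can be picked from up to five unadjusted tests

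*Combined protocol and SAP*

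**What the plan says.** Aim of the Work sets the question without saying what will answer it: "The aim of this study is to assess efficacy and tolerability of Silodosin 4mg vs Dapoxitine 60mg".

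The follow-up text under Methods, item 2 (Clinical Examination), puts two instruments side by side: "patients will be evaluated by PEP (premature ejaculatory profile) & IELT". The assessment is timed as "intravaginal latency time) 2 months after start of treatment". The same section lists four PEP measures: control, distress, satisfaction and interpersonal difficulty. It ends with "satisfaction with sexual intercourse, and interpersonal difficulty related to ejaculation, each assessed on five-point response scales". No total or composite PEP score is defined.

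The Results section says only: "The results will be tabulated, correlated and statistically analyzed to fulfill the aim of the work".

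Statistical analysis offers an independent-samples t-test or a Mann-Whitney test for comparing the groups and gives one criterion: "a p-value is deemed significant if it is less than 0.05".

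Nowhere does the document call an outcome primary, rank outcomes, set a testing order or adjust for multiple tests. There is no sample-size calculation from which a primary outcome could be inferred.

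**The concern.** Several efficacy outcomes share one per-test threshold and nothing says which of them decides. If IELT favours one drug and a PEP measure favours the other, or only one of them reaches significance, the plan does not say what the efficacy conclusion would be. It also does not say whether the four PEP measures are tested separately or combined.

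The practical risk is selection after the fact. The report could rest on whichever of up to five comparisons falls below 0.05, and a reader could not tell that choice from a planned one. Under that practice the 5% level describes each test but not the efficacy conclusion.

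**Working it through.** **The plan's own figure.** The only error rate in the document is the 0.05 threshold. It is declared, not derived, and it is the false-positive rate of a single test, so there is no calculation to reproduce.

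**Inputs**
- Threshold 0.05 per test (Statistical analysis). Sidedness is not stated; two-sided is assumed, so the critical value is c = 1.96.
- Number of tests k: IELT plus four PEP measures gives k = 5; IELT plus one PEP score gives k = 2 (Clinical Examination). Separate testing of the PEP measures is an inference.
- Decision rule: any significant result counts as an efficacy difference. This is assumed, as the plan states no rule.
- Correlation ρ between the test statistics: not given, so varied.
- No true difference on any outcome. A false difference in either direction is counted.

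**Formula.** For uncorrelated tests, the risk is 1 − (1 − 0.05)^k:
- k = 5: 1 − 0.95^5 = 0.226
- k = 2: 1 − 0.95^2 = 0.0975

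For a common correlation ρ (one-factor normal model):

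risk = 1 − ∫ φ(u) · [Φ((c − √ρ·u)/√(1−ρ)) − Φ((−c − √ρ·u)/√(1−ρ))]^k du

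| ρ | Five tests | Two tests |
|---|---|---|
| 0 | 22.6% | 9.8% |
| 0.5 | 18.3% | 9.1% |
| 0.7 | 14.8% | 8.3% |
| 0.9 | 10.2% | 7.0% |
| 0.95 | 8.5% | 6.5% |
| 0.99 | 6.5% | 5.7% |

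Both columns reach 5% only in the limit ρ = 1.

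**Unequal correlations.** IELT may correlate less with the PEP measures than they do with each other. Simulating five tests with IELT–PEP correlation from 0 to 0.7 and PEP–PEP correlation from 0.3 to 0.9 (valid combinations only) gives 11.9% (0.7 and 0.9) to 21.5% (0 and 0.3).

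**Small-sample check.** Simulated t-tests (20,000 runs, five outcomes) at ρ = 0, 0.5 and 0.9 gave 22.8%, 18.4% and 10.3% with 40 per arm, and 23.0%, 17.7% and 10.3% with 25 per arm. The document gives both 80 patients (Study design) and 50 (Patients and Methods; an equal split is assumed). That discrepancy has almost no effect on these error rates.

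**A different rule.** If IELT and a single PEP score both had to be significant, the risk would be 2 × 0.05 minus the two-test figure: 0.10 − 0.0975 = 0.25% at ρ = 0, and 0.10 − 0.0704 = 3.0% at ρ = 0.9.

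**The case against.** The strongest reply is that the percentages are not a property of this plan. They need three things the document does not supply: separate PEP tests, an any-result rule and correlations. Over the scenarios tabulated, the any-result figures run from 5.7% to 22.6%, and a rule requiring both IELT and one PEP score would put the risk below 5%. The plan also never claims family-wise control; it gives a per-test threshold. All of this is correct. It means that the efficacy error rate is undefined as the plan stands and that inflation is one possible consequence. It does not supply the missing decision rule.

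It can also be said that IELT is plainly primary because it defines eligibility: "Patients with primary premature ejaculation (PPE) according to (IELT < 1 min". But an entry criterion is not a declared endpoint. The follow-up text lists PEP first, and the Introduction cites a definition based on distress, which points towards PEP. The document does not settle the choice, and preferring IELT is a judgement.

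Finally, Study design uses the past tense ("We randomly assigned 80 outpatients with PPE to two groups"), but tenses are mixed throughout the document, so this is weak evidence that outcomes have been seen. The advice for that case is therefore conditional.

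**Conclusion.** The concern holds. That no primary efficacy outcome, ranking or multiplicity rule is stated can be read directly from the document and rests on no assumption.

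The size is illustrative. Under an any-significant-result rule with two-sided tests, the chance of at least one false difference is 22.6% to 10.2% for five tests, and 9.8% to 7.0% for two, over assumed correlations of 0 to 0.9. Under that rule the efficacy conclusion is held near 5% only if the outcomes are almost perfectly correlated. Tests on side effects are not counted and would add to the total. The plan should be changed, and the change is cheap.

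**What to change.** Before any outcome data are examined, add to Statistical analysis:

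1. One primary efficacy outcome. IELT at 2 months is the natural choice.
2. One pre-named between-group test for it, from the two already listed, at two-sided 0.05.
3. A statement that the efficacy conclusion rests on this result.
4. The four PEP measures as secondary, either with Holm adjustment across the four or as estimates with 95% confidence intervals and no significance claims.
5. How the IELT value is obtained. If it is recorded per occasion, state one per-patient summary; otherwise use the single 2-month value.

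If outcome data have already been seen, report every efficacy outcome, say that the primary was named afterwards, and present the results as exploratory.

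**Cost.** This needs wording only, with no extra patients and no measurements beyond those planned. A PEP measure alone could no longer carry the headline claim. With Holm, the PEP difference detectable with 80% power (t-test approximation for five-point scales, in SD units) rises as follows:

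| Significance level | 40 per arm | 25 per arm |
|---|---|---|
| 0.05 (unadjusted) | 0.63 | 0.81 |
| 0.025 | 0.70 | 0.90 |
| 0.0167 | 0.74 | 0.94 |
| 0.0125 (strictest Holm step) | 0.76 | 0.98 |

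Reporting confidence intervals only avoids this loss.

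**What remains.** The primary conclusion is held at 5%. If Holm is applied to PEP without first requiring a significant IELT result, the chance of some false significant result among all five outcomes is 1 − 0.95 × 0.9875^4 = 9.7% at correlation 0, 8.3% at 0.5 and 5.5% at 0.9. That is acceptable only because secondary results are barred from deciding efficacy, and the plan should say so.
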